## 6.8. Duration of Subject Participation

Subjects in Cohort 1 will complete the study in approximately 3 months. Subjects in Cohort 2, Arm 3 will complete the study in approximately 4 months; subjects in Cohort 2, Arm 4 will require approximately 3 months. Subjects in Cohort 3 will complete the study in approximately 4 months. The first infusion for all cohorts is defined as Study Day 1. Study Day 15 is the second infusion for Cohort 3. The manufacturing time is currently estimated to be 5 weeks and although accounted for in study participation time, no subject activities are planned during this time. Screening and baseline assessment and informed consent visits will require approximately 2 hours. Final eligibility assessments and WB collection or plasmapheresis will require approximately 4 hours. On the day of infusion, the infusion and post-infusion studies will require approximately 8 hours.

For all cohorts, the on-site follow-up assessments will take 1 to 2 hours to complete, and the telephone assessments will take 15 to 20 minutes to complete. Cohorts 1 and 2 will have on-site follow-up assessments on Study Days 2, 8, and 29 and telephone follow-up assessments on Study Days 3, 4, and 15. Cohort 3 will have on-site follow-up assessments on Study Days 2, 8, 16, 22, and 43 and telephone follow-up assessments on Study Days 3, 4, 17, 18, and 29.

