### 8.3.4. 28-Day Follow-Up Visit

A post-infusion follow-up visit will be scheduled 28 days ( $\pm$  1 day) post-infusion for subjects enrolled in Cohorts 1 and 2. For subjects enrolled in Cohort 3, a 28-day post-infusion follow-up visit will take place after the second plasma infusion, only, approximately 42 days after the first infusion visit. The following procedures will be performed at these follow-up visits:

- Review of medical history, concomitant medications, and AEs since the 14-day telephone follow-up contact;
- Abbreviated physical exam which includes vital signs (blood pressure, heart rate, respiration rate, and temperature) and a general assessment of health;
- Collect blood samples as noted for all tests listed in the Schedule of Events tables (Table 4, Table 5, Table 6, and Table 8); and
- Exit interview concluding the subject's study participation.

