1.2 Aims

1.2.1 Primary Objectives

The primary objective of this study is to assess the safety of single infusions with the RePlas™ FDP product at increasing fixed doses of either one unit (approximately 270 mL), two units (approximately 540 mL), or three units (approximately 810 mL) in normal healthy subjects.

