2.2.3 Infusion Visit(s)

The infusion visit for the first subject in each cohort is to occur approximately five weeks following his or her last collection visit. Unlike Cohorts 1 and 2 subjects, Cohort 3 subjects require two infusion visits. These are to occur with no less than a two-week interval in between infusions. Subjects will undergo autologous infusion at each of these visits according to the corresponding treatment specifications of the arm to which they belong.

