2.2.4 Follow-up Visits

Post-infusion, subject assessments are to occur at scheduled in-person and telephone follow-up visits. For Cohorts 1 and 2, in-person post-infusion visits will occur on Study Days 2, 8, and 29, which corresponds to conducting assessments 24 hours, 7 days, and 28 days post-infusion. These visits will take one to two hours. Telephone follow-up visits of a 15 to 20 minute duration are to occur on Study Days 3, 4 and 15, or 48 hours, 72 hours, and 14 days post-infusion.

Follow-up visits for Cohort 3 subjects subsequent to the first infusion visit are the same as those scheduled for Cohorts 1 and 2. However, on Study Day 15, Cohort 3 subjects will undergo the second infusion and accompanying follow-up visits for this infusion are spaced in time to occur as those performed for Cohorts 1 and 2. Cohort 3 in-person follow-up visits will be scheduled for Study Days 2, 8, 16, 22, and 43 and take 1 to 2 hours to complete. The telephone follow-up visits, each taking approximately 15 to 20 minutes to complete, will be conducted on Study Days 3, 4, 17, 18, and 29.

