4.5.3 Conduct Safety Analyses (Primary Objective)

To provide the DSMB with formal safety reports for review, analyses required to generate Table 1.1 – Table 8.3 and Figures 1 and 2 will be conducted as prescribed in the FDP-1 DSMB Charter, except for Tables 7.4-7.6. For Cohort 3, Open and Closed session tables will be created. The Open session tables will present overall totals for Cohort 3. The Closed session tables will present the data by masked treatment arm (A or B).

Safety data will be summarized for each cohort using standard descriptive statistics.

- For quantitative variables, the following statistics will be provided:
 - Number of subjects;
 - Mean;
 - Standard deviation, minimum, maximum;
 - Median; and
 - 25th and 75th percentile.
- For categorical variables, percentages will be calculated using the number of subjects with non-missing data for the specific variable.

AEs will be coded using the most recent version of the Medical Dictionary of Regulatory Activities preferred terms and will be grouped by system, organ, and class designation. AEs will be summarized using standard FDA-recommended templates distinguishing those defined as TEAEs. A TEAE will be defined as an AE that emerges during or following treatment (infusion), having been absent pretreatment. For all TEAEs, relatedness to infused product will be presented. TEAEs related to study treatment will be defined as definitely or probably related to study treatment. A SUSAR will be defined as a Suspected, Unexpected, Serious Adverse Reaction. A listing of SUSARs will be provided by USAMMDA upon reconciliation of their SAE database with the Oracle Clinical database.

Use of the Centers for Disease Control National Healthcare Safety Network Hemovigilance Module criteria will ensure consistent definitions are applied when using transfusion-related event terms, such as

transfusion related acute lung injury or transfusion associated circulatory overload. The National Cancer Institute Common Terminology Criteria will be used to assess all event terms (AEs) for toxicity grade, or severity, regardless of whether the event is transfusion-related (HHS-2010). AEs will also be presented by maximum severity or maximum common terminology criteria for AE (CTCAE) grade (depending on collection). A summary of SAEs and a summary of AEs leading to treatment discontinuation will be presented.

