	Cohort 1		Cohort 2		Cohort 3
	FDP-CPD 270 mL (N = XX) n (% ^a)	FDP-ACD 270 mL (N = XX) n (% ^a)	FDP-CPD 540 mL (N = XX) n (% ^a)	FDP-ACD 540 mL (N = XX) n (% ^a)	810 mL (N = XX) n (% ^a)
Adverse Events	xx (xx.x)	xx (xx.x)	xx (xx.x)	xx (xx.x)	xx (xx.x)
Treatment Emergent Adverse Events	xx (xx.x)	xx (xx.x)	xx (xx.x)	xx (xx.x)	xx (xx.x)
Treatment-Emergent Adverse Events Related to Study Treatment	xx (xx.x)	xx (xx.x)	xx (xx.x)	xx (xx.x)	xx (xx.x)
Serious Adverse Events	xx (xx.x)	xx (xx.x)	xx (xx.x)	xx (xx.x)	xx (xx.x)
Adverse Events Leading to Discontinuation of Investigational Product	xx (xx.x)	xx (xx.x)	xx (xx.x)	xx (xx.x)	xx (xx.x)
Fatal Adverse Events	xx (xx.x)	xx (xx.x)	xx (xx.x)	xx (xx.x)	xx (xx.x)

Notes: Subjects may be counted in more than one row.

^a=Denominator for each % is the treatment group N.

Table 2.16. - Table 2.20 (Closed). Overview of Subject Incidence of AEs - Overall
Subject Incidence of AEs – Overall
Full Analysis Population – F1 (N=XX)
FDP-1
Phase I

	Cohort 1		Cohort 2		Cohort 3	
	FDP-CPD 270 mL (N = XX) n (% ^a)	FDP-ACD 270 mL (N = XX) n (% ^a)	FDP-CPD 540 mL (N = XX) n (% ^a)	FDP-ACD 540 mL (N = XX) n (% ^a)	A 810 mL (N = XX) n (% ^a)	B 810 mL (N = XX) n (% ^a)
Adverse Events	xx (xx.x)	xx (xx.x)	xx (xx.x)	xx (xx.x)	xx (xx.x)	xx (xx.x)
Treatment Emergent Adverse Events	xx (xx.x)	xx (xx.x)	xx (xx.x)	xx (xx.x)	xx (xx.x)	xx (xx.x)
Treatment-Emergent Adverse Events Related to Study Treatment	xx (xx.x)	xx (xx.x)	xx (xx.x)	xx (xx.x)	xx (xx.x)	xx (xx.x)
Serious Adverse Events	xx (xx.x)	xx (xx.x)	xx (xx.x)	xx (xx.x)	xx (xx.x)	xx (xx.x)
Adverse Events Leading to Discontinuation of Investigational Product	xx (xx.x)	xx (xx.x)	xx (xx.x)	xx (xx.x)	xx (xx.x)	xx (xx.x)
Fatal Adverse Events	xx (xx.x)	xx (xx.x)	xx (xx.x)	xx (xx.x)	xx (xx.x)	xx (xx.x)

Programming Note: The table will be repeated for all analysis populations that are determined to be on a different set of subjects as described in Section 4.2 (Table 2.17 – Table 2.20). All tables may not be produced based on the table reduction method mentioned in Section 4.2 and may not exactly match the SAP. The titles for the tables will be the same for the other populations with the name of the population changing based on the population being used.

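### The overall TEAE and SAE tables set one infusion and 28 days in Cohorts 1-2 beside two infusions and 42 days in Cohort 3, which inflates expected incidence at 810 mL by one step even with no dose effect

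*SAP*

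**What the plan says.** SAP 1.2.1 frames the primary aim by dose and by single infusion: "The primary objective of this study is to assess the safety of single infusions with the RePlas™ FDP product at increasing fixed doses".

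The tables that serve a comparison across doses are in SAP section 5: "Table 2.16. - Table 2.20 (Closed). Overview of Subject Incidence of AEs - Overall", with the same arrangement in Tables 3.10-3.12 (TEAEs by preferred term) and 7.1-7.3 (SAEs). Every cell is a number and percentage of subjects, and the denominator is the group N. Cohort 3 appears as one total in the Open version and as masked arms A and B in the Closed version. At final analysis those arms are relabelled by sequence, FDP then FFP and FFP then FDP. No shell has a per-infusion denominator, person-time, a common window or a note on exposure.

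Exposure differs by cohort:
- **Infusions (SAP 2.2.3):** "Unlike Cohorts 1 and 2 subjects, Cohort 3 subjects require two infusion visits".
- **Follow-up, Cohorts 1-2 (SAP 2.2.4):** visits on Study Days 2, 8 and 29, "which corresponds to conducting assessments 24 hours, 7 days, and 28 days post-infusion".
- **Follow-up, Cohort 3 (SAP 2.2.4):** "Cohort 3 in-person follow-up visits will be scheduled for Study Days 2, 8, 16, 22, and 43". Protocol 6.8 gives the same days, and protocol 8.3.4 places the 28-day visit "after the second plasma infusion, only, approximately 42 days after the first infusion visit".

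SAP 4.5.3.1 and protocol 11.1.1 say that Cohort 3 primary safety data will be shown by product, and that events within 14 days will generally be attributed to the latest product. None of these shells has a product column.

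**The concern.** Someone reading across these tables will take the 810 mL columns as the safety record of 3 units of FDP. They are not. They cover about 1,620 mL over two visits, half of it the control product, and a follow-up half as long again as at the lower doses. Any non-zero background or per-infusion event rate then raises expected incidence at 810 mL.

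The TEAE and SAE tables go to the DSMB, which advises after Cohort 3 on the next FDP trial. Protocol 6.1 rests the safety conclusion on TEAEs alone. In columns this small, one extra affected subject from the second infusion or the extra two weeks could be read as a dose signal.

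**Working it through.** **The plan's own figure.** The documents give no expected value for these tables. Their only related calculation is the precision table (SAP Table 3, protocol Table 16). Clopper-Pearson limits at 10% in 24 subjects come out at 1.6-29.2%, width 27.6, as stated. The other eight cells also reproduce.

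**Inputs from the documents.** Cohorts 1-2: one infusion, 28 days. Cohort 3: two infusions, 42 days (14 after the first, 28 after the second). Arms have 4 subjects and the Cohort 3 total is 8.

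**Assumptions.** A constant background risk b per 28 days of at least one event, a reaction risk r per infusion that is the same for every dose and both products, and independence. Neither rate is in the documents. The central case is b = 20%, r = 10%; the range is b = 10-40%, r = 5-20%.

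**Formulas under no dose effect.**
- Cohorts 1-2: 1 - (1-b)(1-r)
- Cohort 3: 1 - (1-b)^1.5 × (1-r)^2, since 42/28 = 1.5

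**Central case.**
- Cohorts 1-2: 1 - 0.8 × 0.9 = 28.0%
- Cohort 3: 1 - 0.7155 × 0.81 = 42.0%, a gap of 14.0 points
- Longer window alone: 1 - 0.7155 × 0.9 = 35.6%, or +7.6 points
- Second (FFP) infusion alone: 1 - 0.8 × 0.81 = 35.2%, or +7.2 points

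The two parts overlap slightly, so they sum to a little more than 14.0.

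**Range.**

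| b | r | Cohorts 1-2 | Cohort 3 | Gap (points) |
|---|---|---|---|---|
| 10% | 5% | 14.5% | 22.9% | 8.4 |
| 10% | 20% | 28.0% | 45.4% | 17.4 |
| 40% | 5% | 43.0% | 58.1% | 15.1 |
| 40% | 20% | 52.0% | 70.3% | 18.3 |

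**Would the by-product rule alone cure it?** No. For FDP given first, 14 days would sit beside 28: 1 - 0.8^0.5 × 0.9 = 19.5% against 28.0%, now a false fall. No attribution rule is stated for days 15-28 after the second infusion.

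**Would a common window cure it?** Yes. From the FDP infusion through 7 days, every dose has 1 - 0.8^0.25 × 0.9 = 14.9%.

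**What would be seen in small columns?** Expected counts are 4 × 0.28 = 1.1 and 4 × 0.42 = 1.7. A 4-subject Cohort 3 column would exceed a 4-subject Cohort 1-2 column with probability 52%, against 34% if exposure were equal.

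**All-AE row of Tables 2.16-2.20.** Protocol 10.5.1 starts AE collection at plasma collection. SAP 2.2.2 requires 3 to 4 successful donations in Cohort 3, against one in Arms 1, 2 and 4 and two in Arm 3. At an assumed 5% risk per donation, the chance of a donation AE is 5.0% with one, 9.8% with two, 14.3% with three and 18.5% with four.

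**The case against.** The strongest reply has four parts.

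**The stronger readings go too far.** A reader might infer that incidence will climb across all three doses, that escalation decisions are distorted, or that a flat dose-response will necessarily look like a rise. The documents do not support these. Cohorts 1 and 2 have identical infusions and follow-up, so their TEAE rows are comparable. No Cohort 3 data exist when either escalation decision is made. The artefact is one step at 810 mL, in expectation. In the central case a 4-subject Cohort 3 column fails to exceed its neighbour about 48% of the time. This part stands in full.

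**An FDP-only count could break the blind.** Open tables are made by blinded programmers, and the Closed tables deliberately show only A and B. Isolating the FDP period requires knowing which infusion was FDP. This stands, and it confines the FDP-only panel to the final unblinded tables.

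**Readers can untangle it, and nothing is tested.** Final labels name the sequence, Listing 8 gives both infusion dates and Listing 13 gives AE start dates. The related-TEAE row should shed much of the background. The bias also overstates risk at 810 mL. All this is true and limits the harm, but no planned summary does the untangling.

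**A 7-day window is a choice.** The plan's attribution unit is 14 days, which would also equalise exposure. However, contact around day 14 is a telephone call in Cohorts 1-2 and after the second infusion, but an infusion visit after the first. The schedule is identical only through day 7 (24, 48 and 72 hours, then the visit). That visit also defines study completion and the minimum DSMB data. Seven days is the cleaner choice, not the only one.

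**Conclusion.** The mismatch is in the documents, and its direction is certain for any non-zero background or per-infusion rate. Its size depends on rates that the documents do not give: 14 points in the central case, and about 8 to 18 over the range tried. Roughly half comes from the longer window and half from the FFP infusion. The calculation assumes a constant background rate, equal reaction risk per infusion and independence. Protocol 10.5.1 extends AE collection 7 days past the last sample. If that applies to every cohort, the windows become 35 and 49 days, and the direction is unchanged.

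The consequence is limited to the 810 mL columns of the overall TEAE and SAE tables, and so to the review after Cohort 3 and the final report. This is a fault of presentation in a descriptive study, worth correcting because the correction is cheap.

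**What to change.** **Final, unblinded tables (2.16-2.20, 3.10-3.12, 7.1-7.3).** Add a cross-dose panel counting TEAEs (serious ones in 7.1-7.3) from the start of the FDP infusion through the 7-day visit in every cohort, using only the FDP period in Cohort 3. Keep the whole-follow-up counts as a second panel.

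**Masked DSMB tables.** Do not split by product. State the number of infusions and the days at risk in each column header. Show Cohort 3 counts through 7 days by infusion number, as a total in Open and by A and B in Closed. Blinded programmers can produce the Open counts without the randomization code.

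**Tables 8.1-8.3.** Leave discontinuations on whole follow-up. A 7-day cut could drop a day 8-14 event that prevents the second infusion.

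**Text.** Reconcile the by-product statement in SAP 4.5.3.1 and protocol 11.1.1 with the sequence columns in the shells.

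**Cost.** One extra panel per table, from data already collected. Two downsides should be stated: events after day 7 appear only in the second panel, and in Arm 6 late effects of FFP can fall inside the FDP window.

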#### 6. TRIAL OBJECTIVES AND PURPOSE

## 6.1. Primary Objective

The primary objective of this study is to assess the safety of single infusions with the RePlasTM FDP product at increasing fixed doses of either 1 unit (approximately 270 mL), 2 units (approximately 540 mL), or 3 units (approximately 810 mL) in normal healthy subjects. In the 2 lower dose cohorts, safety will also be assessed in terms of the type of autologous plasma used as the starting material in the manufacture of the investigational product:

- FDP derived from WB where CPD was used as the anticoagulant, or FDP-CPD; and
- FDP collected by plasmapheresis where ACD was used as the anticoagulant, or FDP-ACD.

The highest dose cohort will receive FDP manufactured only from FFP collected by plasmapheresis (FDP-ACD). Conclusions on whether the study meets its safety objectives will be based only on treatment emergent adverse events (TEAEs). These are adverse events (AEs) that occur after treatment (plasma infusion) has begun and throughout the study's post-infusion follow-up period.

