The timeframe for the collection of AEs will begin at plasma collection and will continue through 7 days after the last required sample collection (Day 29). Any AE, regardless of its relationship to study product, will be recorded in the AE section of the eCRF. However, any AE that occurs after the informed consent is signed, but before the first infusion visit, will be recorded as medical history, unless it is related to a study procedure. AEs associated with a study procedure (eg, blood or plasma donation) will be recorded in the AE section of the eCRF.

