# 11.1.1. Endpoints for Primary Study Objective Analyses

The primary endpoints for the study to be assessed are specifically:

- TEAEs;
- SAEs:

- Suspected, unexpected, serious adverse reactions (SUSARs); and
- Deaths.

Safety endpoints for subjects' that will be assessed just prior to infusion and again after infusion include evaluations presented in sections 8.2 and 8.3.

Descriptive statistics will be used to analyze the primary safety endpoints. Tables produced to exhibit the primary safety endpoint data will be presented by the specific type of plasma product infused. In Cohorts 1 and 2, this data will be presented by FDP product type, FDP-ACD and FDP-CPD; in Cohort 3 by experimental product and control product, FDP-ACD and FFP. The primary safety data reported to the DSMB for Cohort 3 will be masked. Unblinding during the study will only occur in accordance with section 6.6.3.

In general, AEs that occur in Cohort 3 subjects within 14 days after infusion will be attributed to the most recently infused product. However, there may be exceptions to use of this temporal attribution rule to all transfusion-related AEs given the possibility that those AEs that occur after infusion with the second product may potentially be related to infusion with the first infusion product (e.g., an immunogenic response).

The safety endpoints measured prior to the infusion will serve as the "baseline" to which all subsequent measurements will be compared.

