2. SAFETY

The safety of infusion with the experimental product will be determined by observation of treatment emergent adverse events (TEAEs), defined as only AEs that occur after starting the trial infusion administration. In addition to TEAEs, safety will be evaluated based on the occurrence of SAEs, suspected unexpected serious adverse reactions (SUSARs), and deaths. Safety assessment in Cohorts 1 and 2 subjects will examine the cohort-specific product infusion dose and the specific FDP product type infused (e.g., FDP-CPD or FDP-ACD). The safety assessment performed in Cohort 3 subjects will assess treatment with FDP at the highest fixed infusion dose (approximately 810 mL) and compare, within the same subject, the treatment safety of FDP versus FFP at the equivalent dose.

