4.5.3.1 Primary Safety Endpoints

The primary safety endpoints to be assessed are AEs, specifically:

- TEAEs;
- SAEs;
- SUSARs; and
- Deaths.

Descriptive statistics will be used to analyze the primary safety endpoints. Tables produced to exhibit the primary safety endpoint data will be presented by the specific type of plasma product infused. In Cohorts 1 and 2, this data will be presented by FDP product type, FDP-ACD and FDP-CPD; in Cohort 3 by experimental product and control product, FDP and FFP. The primary safety data reported to the DSMB for Cohort 3 will be masked. Unblinding during the study will only occur in accordance with Section 3.3.2 following Westat's SOP DA-504 Development of a Plan for Randomization, Masking, and Unmasking.

In general, AEs that occur in Cohort 3 subjects within 14 days after infusion will be attributed to the most recently infused product. However, there may be exceptions to use of this temporal attribution rule to all transfusion-related AEs given the possibility that those AEs that occur after infusion with the second product may potentially be related to infusion with the first infusion product (e.g., an immunogenic response).

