^c=Denominator adjusted because gender-specific event for females: N=XX (FDP-CPD), N=XX (FDP-ACD) for Cohort 1; N=XX (FDP-CPD), N=XX (FDP-ACD) for Cohort 2; N=XX (810 mL) for Cohort 3 (Open Session); N=XX (A), N=XX (B), N=XX for Cohort 3 (Closed Session) [for applicable PTs].

Preferred Terms within System Organ Class are sorted in descending order of frequency based on the TEAE category.

to reflect total counts. For the Closed session, the treatment arms will be masked as A and B as shown above. The table numbers will have the word “(Closed)” after the table number before the decimal. Closed session tables will be produced by the unblinded programmers. Final data analysis for Cohort 3 will use the labels FDP-ACDxFFP and FFPxFDP-ACD for the treatments after the study is unblinded and the word “(Closed)” will be removed from the table number.

Notes: Subjects are counted at most once on each row. Subjects may be included on more than one row.

^a=Denominator for each % is the treatment group N.

^b=Denominator adjusted because gender-specific event for males: N=XX (FDP-CPD), N=XX (FDP-ACD) for Cohort 1; N=XX (FDP-CPD), N=XX (FDP-ACD) for Cohort 2; N=XX (810 mL) for Cohort 3 (Open Session); N=XX (A), N=XX (B) for Cohort 3 (Closed Session) [for applicable PTs].

^c=Denominator adjusted because gender-specific event for females: N=XX (FDP-CPD), N=XX (FDP-ACD) for Cohort 1; N=XX (FDP-CPD), N=XX (FDP-ACD) for Cohort 2; N=XX (810 mL) for Cohort 3 (Open Session); N=XX (A), N=XX (B), N=XX for Cohort 3 (Closed Session) [for applicable PTs].

Preferred Terms within System Organ Class are sorted in descending order of frequency based on the TEAE category.

50

Program Path:

Data Source: ADAE Cross Reference: Listing 13

Data Extract Date:

Table 4.1. - Table 4.9. Summary of TEAEs and TEAEs by Relatedness per Investigator by Preferred Term in Descending Frequency within System Organ Class

Subject Incidence of TEAEs and TEAEs Relatedness per Investigator – Cohort 1 (270 mL)
Safety Population – S1 (N=XX)

FDP-1

Phase I

System Organ Class Preferred Term	TEAEs		TEAEs Considered Not Related per Investigator		TEAEs Considered Unlikely Related per Investigator		TEAEs Considered Possibly Related per Investigator		TEAEs Considered Probably Related per Investigator		TEAEs Considered Definitely Related per Investigator	

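### The final Cohort 3 adverse-event tables are columned by treatment sequence, not by product infused, so no planned table shows the TEAEs of FDP at about 810 mL apart from those of FFP

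*SAP*

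**What the plan says.** Protocol 11.1.1 sets the layout of the primary safety tables: "Tables produced to exhibit the primary safety endpoint data will be presented by the specific type of plasma product infused". SAP 4.5.3.1 repeats this and names the Cohort 3 columns: "in Cohort 3 by experimental product and control product, FDP and FFP". SAP 2 adds that the Cohort 3 safety assessment will "compare, within the same subject, the treatment safety of FDP versus FFP at the equivalent dose".

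To support a product layout, both documents give an attribution rule. In general, "AEs that occur in Cohort 3 subjects within 14 days after infusion will be attributed to the most recently infused product", with exceptions allowed for effects that may trace back to the first product.

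The shells in SAP 5 do not follow this layout. For the final analysis, the notes under Tables 2 to 8 state: "Final data analysis for Cohort 3 will use the labels FDP-ACDxFFP and FFPxFDP-ACD for the treatments after the study is unblinded" (some notes print FPP for FFP). The SUSAR shell, Tables 7.4 to 7.6, which is produced only at final analysis, prints the two sequence headings directly.

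**The concern.** Protocol 6.1 rests the conclusion on the safety objectives on TEAEs alone, and FDP at about 810 mL is one of the three doses in the primary objective. Cohort 3 is a crossover, so a sequence column pools the period after FDP with the period after FFP. If the shells are programmed as written, no table shows what happened after FDP at the highest dose, and none sets it beside FFP. With no hypothesis tests planned, the descriptive tables are the analysis, and the attribution rule has no table to feed.

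**Working it through.** The plan gives no figure to reproduce. The check compares text with shells, then works out what a sequence column can show.

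**1. Text against shells (Cohort 3, final analysis)**

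| Source | Columns |
|---|---|
| Protocol 11.1.1 | FDP-ACD, FFP |
| SAP 4.5.3.1 | FDP, FFP |
| SAP 5, Tables 2 to 6, 7.1 to 7.3 and 8 (notes) | FDP-ACDxFFP, FFPxFDP-ACD |
| SAP 5, Tables 7.4 to 7.6 (shell) | FDP-ACD X FFP, FFP X FDP-ACD |

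SAP 4.5.4 defines these labels as Sequence 1 and Sequence 2. The same labels head the Cohort 3 baseline demographic tables, so they cannot mean products. No adverse-event table is split by infusion or period.

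**2. What a sequence column shows**

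Inputs: 4 subjects per sequence, each infused with both products (Protocol 5.7; SAP Table 1). The tables give subject incidence, with a subject counted at most once per row.

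- Event after every FDP infusion and no FFP infusion: Sequence 1 shows 4/4 and Sequence 2 shows 4/4. By product: FDP 8/8, FFP 0/8.
- Event after every FFP infusion and no FDP infusion: again 4/4 and 4/4. By product: FDP 0/8, FFP 8/8.

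In expectation, assuming independent events per infusion and no period or carryover effect, each sequence column estimates 1 − (1 − p_FDP)(1 − p_FFP). This is symmetric in the two products. With illustrative risks of 0.50 and 0.125 it gives 1 − 0.50 × 0.875 = 0.5625 in both columns, whichever product carries the higher risk.

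A less extreme display of 2/4 and 2/4 has 4 affected subjects. Each may have had the event after FDP only, FFP only or both, which gives C(6,2) = 15 possible by-product tables. FDP minus FFP then runs from −4/8 to +4/8, that is −50 to +50 percentage points. This range describes what the table hides when read alone; it is not uncertainty in the data.

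**3. Number of tables with Cohort 3 columns**

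- Before reduction: Tables 2.1–2.15, 5; 2.16–2.20, 5; 3.1–3.9, 3; 3.10–3.12, 3; Tables 4, 5 and 6, 3 each (9); 7.1–7.3, 3; 7.4–7.6, 3; 8.1–8.3, 3. Total 5 + 5 + 3 + 3 + 9 + 3 + 3 + 3 = 34.
- Under the reduction rule in SAP 4.2.2, if F1 = F2 and S1 = S2 = S3: 2 + 2 + 1 + 1 + 3 + 1 + 1 + 1 = 12.
- The F1 and F2 versions of Table 2 (4 before reduction, 2 after) also cover subjects never infused and should stay as they are. That leaves 30, or 10, to change.

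**4. Reach of the attribution rule**

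With infusion 2 on Day 15, the rule reaches Day 15 + 14 = Day 29. With infusion 2 on Day 18 (the +3-day window in Protocol Table 8), Study Days 16 and 17 also fall outside it, because 14 days after infusion 1 is Day 15.

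Adverse events are still collected later. Protocol Table 8 schedules their assessment at the Day 43 visit, and Protocol 8.3.4 has that visit review "AEs since the 14-day telephone follow-up contact". Protocol 10.5.1 ends collection 7 days after the last required sample and gives Day 29. In Cohort 3, Day 29 is only a telephone call, and the last scheduled sample is at the Day 43 visit. An end on Day 29, or on Day 36 (29 + 7), therefore conflicts with the Cohort 3 schedule. The two readings that fit leave 43 − 29 = 14 days, or (43 + 7) − 29 = 21 days, without a rule.

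**The case against.** The strongest reply is that the governing text already specifies product columns. The shells are headed as proposed, the study is descriptive, and a programmer need only follow the text. The listings also help: with eight completing subjects, a reader can match adverse-event start dates in Listing 13 to infusion dates in Listing 8 and place most events. That much stands. But Listings 8 and 13 show dates without times, and Listing 13 has no infusion number, although vital-sign Listings 10 to 12 do. An event dated on the day of infusion 2 cannot be placed, and hand matching is not the table that the text promises. The remark that tables may not exactly match the SAP is tied to the table-reduction rule, not to columns.

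It is also fair that the attribution gap is softer than the column mismatch. The rule is introduced as general, and after infusion 2 the most recent product is a natural default.

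Three stronger readings are tempting but unsupported:

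- **That the DSMB displays are defective too.** Their total and masked A/B columns serve the mask and follow a Charter that is not in the documents. SAP 4.5.3.1 says that these data will be masked.
- **That FDP and FFP are never compared, or that secondary objective 1 is undelivered.** SAP 4.5.4 defines that objective through the measures in SAP Table 5. Laboratory, coagulation and vital-sign outputs for these are split by infusion, by sequence and period, or by product (Tables 9 to 13, Figures 3 and 4). The gap is in the primary adverse-event endpoints.
- **That the trial cannot recover the information.** It records what is needed; only the planned display omits it.

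**Conclusion.** The point holds for the final-analysis adverse-event tables. The shells contradict Protocol 11.1.1 and SAP 4.5.3.1, and as written none of the up to 34 Cohort 3 tables (12 after full reduction) separates FDP from FFP. This is a layout that would hide the product contrast on the endpoint that decides the safety conclusion, so it must be fixed before unblinding. The 4/4 versus 4/4 example assumes eight completers and an extreme event pattern. The 0.5625 illustration assumes independence and no period or carryover effect. The contradiction itself depends on neither. The gap beyond 14 days and the unclear Cohort 3 collection end date are secondary, and the main finding stands without them.

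**What to change.** **Tables.** In the final Cohort 3 tables of treatment-emergent events, add FDP-ACD and FFP columns: Tables 3 to 6, the TEAE rows of Table 2 in S1 to S3, and the treatment-emergent events in Tables 7 and 8. Set each N to the subjects infused with that product in the given safety population. The two Ns can differ in S1 if a subject leaves after infusion 1 and is replaced. Keep sequence as a supportive split. Leave pre-infusion events and the F1 and F2 versions of Table 2 by arm or total, since they have no attributed product.

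**Data.** Add an attributed-product variable to the adverse-event dataset and listings, derived from onset date and time and infusion start time under the 14-day rule.

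**Late events.** Before unblinding, state how events more than 14 days after an infusion are assigned. One option is the most recent product, flagged as late, because follow-up is longer after infusion 2. With full completion to Day 43, this gives each product 4 × 14 + 4 × 28 = 168 subject-days.

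**Collection end date.** Reconcile Protocol 10.5.1 with Protocol Table 8 and 8.3.4 for Cohort 3. The window is set in the protocol, so the SAP alone cannot settle it.

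**Cost.** No new data are needed: Protocol 10.5.1 records adverse-event onset times and Protocol 8.2.2 records infusion start times. The work is up to 30 shell changes (10 after full reduction) and one derived variable. Aligning the shells with Protocol 11.1.1 is an SAP change only. Changing the 14-day rule or the collection window needs a protocol amendment.
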